## **7.2 Serious Adverse Events**

An SAE is any AE meeting the following criteria:

Death	An AE that results in death (note: death due to progression is not an AE/SAE but should be reported as noted in the eCRF completion guidelines).
-------	--

Life-threatening AE	An AE that places the participant, in the view of the Investigator, at immediate risk of death from the AE as it occurred (ie, does not include an AE that had it occurred in a more severe form, might have caused death).
Required or prolonged participant hospitalization	An AE that results in an initial participant hospitalization or prolongs an existing hospitalization of the participant. If a participant is hospitalized as part of the clinical use of the study treatment, the period of normal hospitalization will be based on the Investigator's judgement and experience. Hospitalizations longer than this period will be considered prolonged hospitalizations.
Persistent or significant disability/incapacity	An AE that results in a substantial disruption of a participant's ability to conduct normal life functions.
Congenital anomaly/birth defect	A congenital anomaly/birth defect that occurs in the offspring of a participant exposed to the study drug.
Important medical event	An AE that may not result in death, be life-threatening, or require hospitalization may be considered an SAE when, based upon appropriate medical judgment, the event may jeopardize the participant and may require medical or surgical intervention to prevent 1 of the outcomes listed above. Examples of such "important medical events" include allergic bronchospasm requiring intensive treatment in an emergency room or at home, blood dyscrasias or convulsions that do not result in participant hospitalization, or the development of drug dependency or drug abuse

SAEs must be reported by the Investigator to the Sponsor or designee within 24 h of discovery for all patients from the time of consent, while on study and for 30 days after 1) completion of study participation or 2) if patient is rendered off-study and in the follow-up period only. SAEs will be reported in the eCRF with instruction provided in the eCRF Completion Guidelines.

The Investigator is required to provide an assessment of the causal relationship between the event and the study drug(s) at the time of the initial report. The related SAE page should be completed as thoroughly as possible and signed by the Investigator before transmittal to the Sponsor or designee. The Investigator should not wait to for additional information to fully document the related SAE before notification, although additional information may be requested.

Instances of death, congenital abnormality, or an event that is of such clinical concern as to influence the overall safety assessment, if brought to the attention of the Investigator at any time after cessation of study drug(s) and linked by the Investigator to this study, should be reported to the Sponsor or their designee. Where applicable, information from relevant laboratory results, hospital case records, and autopsy reports should be obtained.

**The SAE/narrative description should include the following, as a minimum:**

- Time to onset following PVSRIFO and/or pembrolizumab infusion, as applicable
- Maximum severity of signs and symptoms
- Treatment(s) undertaken (including dose, route frequency, as applicable)
- Action taken with study drug(s) (eg, permanently discontinued, treatment interruption)
- Concomitant medications at the time of the event(s)
- Time to resolution as the information becomes available

**7.3 Definition of an Unexpected Adverse Event**

An AE or suspected adverse reaction is considered "unexpected" if it is not listed in the current IB or PI or is not listed at the specificity or severity that has been observed previously. In addition, reports which add significant information on specificity or severity of a known already documented AE may constitute an unexpected AE.

The Medical Monitor or designee will evaluate expectedness of all SAEs as per the currently available safety information. For all events, medical and scientific judgement should be exercised in deciding whether expedited reporting is appropriate in other situations and should consult with the Sponsor Medical Monitor or designee if unclear.

**7.4 Assessment and Definition of Dose Limiting Toxicity**

For this study, assessment of treatment emergent DLT will occur after a patient receives PVSRIFO and until 21 days ( $\pm$  3 days) after the first dose of pembrolizumab.

Peritumoral and CE occur frequently in rGBM and may be secondary to the disease process itself, surgical procedures, necrosis from previous radiation, or inflammation due to immune infiltration of the brain or destruction of tumor cells, which may manifest as neurologic dysfunction. Given that transient PTE has been observed following PVSRIFO use, the primary focus for DLT will be neurologic events meeting the criteria for a DLT defined as follows:

1.  $\geq$  Grade 3 neurologic events related to PTE or CE within the first 3 weeks of the first pembrolizumab administration that:
  - a. Do not resolve to  $\leq$  Grade 1 with the management practices outlined herein ( $\leq$  4mg/dexamethasone or 7.5 mg/kg bevacizumab) within 3 weeks of initiating such treatments,

and/or

- b. Require surgical debulking of the PVSRIFO infused tumor within 3 weeks of the first pembrolizumab administration

**To assess for any other potential DLT, CTCAE v5.0 will be utilized, and the following will also be considered DLT if treatment related:**

1. Any of the following SAEs:
  - a. Treatment-related death
  - b. Treatment-related life-threatening event
  - c. A medically significant condition (defined as an event that compromises patient safety or may require medical or surgical intervention to prevent one of the outcomes above).
  - d. Requires inpatient hospitalization or prolongation of existing hospitalization
  - e. Results in persistent or significant incapacity or substantial disruption to conduct normal life functions
2. Any Grade 4 non-hematologic toxicity
3. Any Grade 3 non-laboratory-based toxicity that is not reversible to its pre-PVSRIPO treatment baseline within 2 weeks of onset with the following exceptions:
  - a. Grade 3 fatigue lasting  $\leq$  3 days or Grade 3 fatigue in a participant with Grade 1 fatigue at baseline
  - b. Grade 3 diarrhea, nausea, or vomiting without use of anti-emetics or anti-diarrheals per standard of care
  - c. Grade 3 adrenal insufficiency due to suboptimal steroid replacement therapy
  - d. Grade 3 rash without use of corticosteroids or anti-inflammatory agents per standard of care
4. Grade 3 or Grade 4 non-hematological laboratory values only if meets one of the serious criteria outlined in 1 above or:
  - a. The abnormality persists for  $>$  1 week
  - b. The abnormality results in a drug-induced liver injury

**Note:** Treatment-emergent, non-clinically significant laboratory abnormalities that are treatable with routine measures, or reversible ( $\leq$  1 week of onset) laboratory abnormalities in and of themselves (including liver function tests, uric acid, etc.), are not considered DLT.

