## 3 Study Design

To establish therapeutic intent and adequately assess the risk/benefit profile, in the first protocol amendment, the study sample size was adjusted to allow for sufficient statistical power to demonstrate a meaningful difference in response, relative to monotherapy, and efficacy was elevated to a primary endpoint.

This is an open-label, single-arm, non-randomized study characterizing the efficacy, safety and tolerability of PVSRIPO delivered via intratumoral infusion followed by pembrolizumab in patients with rGBM.

Approximately 30 eligible participants, 18 years of age or older, will be enrolled and treated with PVSRIPO and at least a single dose of pembrolizumab in this study. The maximum planned duration of follow-up in this study is up to 24 months (104 weeks), and consists of the following treatments:

- Single PVSRIPO infusion at baseline.
  - Note: retreatment with PVSRIPO is allowed for qualifying patients with enhancing disease  $\geq$  12 months from initial PVSRIPO infusion
- Pembrolizumab (200 mg IV infusion) initiated 14 days after PVSRIPO infusion (up to 28 days, if necessary), given q 3 weeks, through Week 104 (23.5 months of treatment) or until irAE meeting criteria for dose interruption/discontinuation or confirmed progression (must consider clinical and radiographic assessments as outlined in **Section 8.4.6.1** and **Table 3**)

Patients reaching 24 months on this study may be offered participation in a longer-term follow-up/PVSRIPO retreatment protocol or other mechanisms.

The study will occur in the following periods as outlined in **Table 1** and **Figure 1**.

- Screening Period 1: Between 1 and 6 weeks prior to catheter placement
- Screening Period 2: Within 7 days of catheter placement
- PVSRIPO Catheter Placement and Biopsy (if required) Period: Day 0
- PVSRIPO Infusion Period/Baseline: Single PVSRIPO infusion at Day 0 or Day 1 (unless extension granted by Sponsor)
- Post-PVSRIPO infusion, pembrolizumab treatment and follow-up Period: pembrolizumab starting at Week 2 (up to Week 4, max) and every 3 weeks thereafter, to a maximum of Week 104 (approximately 23.5 months maximum pembrolizumab treatment duration)

Participants with enhancing disease  $\geq$  12 months from a prior PVSRIPO infusion and meet the key IC/EC for retreatment will be eligible for additional PVSRIPO infusion(s).

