### **3.1 Safety Run-in and DLT Assessment**

This study will start with a safety run-in period. The first 3 participants will be sequentially enrolled, with a mandatory waiting period of 21 to 28 days after the immediate prior patient's PVSRIPO treatment before the next patient receives PVSRIPO. The 21- to 28-day waiting period also applies after the third patient receives PVSRIPO, prior to PVSRIPO treatment of the fourth patient.

The DLT evaluation period for the first 3 patients will begin once a patient who received PVSRIPO receives the first dose of pembrolizumab and continue for 21 days ( $\pm$  3 days to

account for variations in patient visit scheduling, weekends, etc.) after this first dose of pembrolizumab. This wait period allows sufficient time for safety review prior to the next patient receiving their first dose of pembrolizumab. If  $\geq 2$  of the first 3 patients treated with PVSRIPO followed by 1 dose of pembrolizumab experience a DLT, accrual will be halted, and the treatment plan may be modified, or the study may be closed.

If no DLT occurs in the first 3 participants, the dosing regimen will continue as planned and an additional 27 participants will be enrolled to further characterize safety and anti-tumor activity of treatment with PVSRIPO plus pembrolizumab.

However, if only 1 patient experiences a DLT of the first 3 participants treated, an additional 3 participants will be enrolled (without a waiting period between participants) to undergo DLT evaluation. If  $\leq 33\%$  of participants (ie,  $\leq 2$  of 6 total) experience a DLT, the 24 remaining participants will be enrolled. If  $> 33\%$  of participants (ie,  $\geq 3$  of 6) experience a DLT, the study will be halted, and the treatment plan modified, or the study may be closed. After the DLT evaluation period, ongoing monitoring of TEAEs will occur on at least a monthly basis by the Sponsor safety review team and by the DSMB, as specified in the safety plan and applicable charter, respectively.

If one of the first 3 (or 6) participants accrued withdraws from the study during the DLT evaluation period for reasons unrelated to the occurrence of a DLT, the participant will be replaced for the purpose of the initial DLT assessment. For details regarding events and criteria for meeting the definition of a DLT, see [Section 7.4](#).

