**All assessments should occur before the planned pembrolizumab administration.**

**Clinical assessment:**

- Physical examination
- Neurologic and NANO assessment
- KPS
- PRO Assessment
- AE assessment
- Final DLT assessment (Day 21 ( $\pm$  3 days) post- 1st pembrolizumab treatment) for the first 3 to 6 patients, as applicable, if received 1st dose at Week 2, as scheduled

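### The DLT assessment labelled final closes at Day 21 (±3) after first pembrolizumab, before the 3-week and 2-week clocks in the DLT definition must have ended, and no rule says how an open event counts at the enrollment gate

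*Protocol*

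**What the plan says.** **When the assessment ends.** Protocol Section 7.4 states that "assessment of treatment emergent DLT will occur after a patient receives PVSRIFO and until 21 days" (±3) after the first pembrolizumab dose. Section 3.1 gives the same end point. Section 5.3.2 (Visit 6, Week 5) lists "Final DLT assessment (Day 21" (±3 days) for the first 3 to 6 patients.

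**What counts as a DLT.** Criterion 1 in Section 7.4 covers Grade 3 or higher "neurologic events related to PTE or CE within the first 3 weeks of the first pembrolizumab administration that" satisfy 1a or 1b.
- 1a: no resolution to Grade 1 or lower under the described management "within 3 weeks of initiating such treatments".
- 1b: the events "Require surgical debulking of the PVSRIFO infused tumor within 3 weeks of the first pembrolizumab administration".

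A second list applies to treatment-related events. Its item 3 is "Any Grade 3 non-laboratory-based toxicity that is not reversible to its pre-PVSRIPO treatment baseline within 2 weeks of onset", with exceptions. Item 4a covers certain laboratory abnormalities that last more than 1 week. Items 1a to 1e (serious events, including hospitalization) and item 2 (Grade 4 non-hematologic toxicity) carry no clock.

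**What the count decides.** Section 3.1: "If no DLT occurs in the first 3 participants, the dosing regimen will continue as planned and an additional 27 participants will be enrolled". One DLT in three adds three patients, with no wait between them. Two or more in three halts accrual. At most 2 of 6 proceeds, and 3 or more of 6 halts. (The Synopsis words the first stage differently; Section 3.1 is used here.)

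SAP Section 3.2.6 repeats the criteria without an assessment cut-off or a rule for open events.

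**The concern.** Criterion 1a allows onset at any time in the 3 weeks after first pembrolizumab and then allows 3 weeks of treatment before the event can be classified. The assessment that feeds the enrollment decision stops at the end of the first of those two periods. The protocol therefore sets a cut-off that can fall before its own definition can be applied, and it is silent on what happens to an event caught between the two.

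Section 7.4 names neurologic edema events as the main focus of DLT assessment. The only earlier use of the combination cited is four compassionate-use patients (Section 1.2.3), so the lead-in is the main structured safety check before wider enrollment. Two sites, or the sponsor and the DSMB, could classify the same open event differently. SAP Table 14.3.1.8 could also later report a DLT that was not counted at the gate.

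**Working it through.** **Inputs.** First pembrolizumab on Day 14 to 28 after PVSRIPO (Section 3). Call at 21 (±3) days after first pembrolizumab (Sections 3.1, 5.3.2, 7.4). Clocks of 3 weeks (1a), 2 weeks (item 3) and more than 1 week (item 4a) (Section 7.4). Stagger of 21 to 28 days between PVSRIPO infusions for the first three patients (Section 3.1). Assumption: treatment for a 1a event starts on the day of onset. A later start lengthens the gap.

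**1. The plan's own date.** 14 + 21 = Day 35 after PVSRIPO = Week 5. This reproduces Visit 6. A first dose on Day 28 gives 28 + 21 = Day 49.

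**2. One patient's clocks.** Days are counted from first pembrolizumab; onset is on Day t.

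| Criterion | Decided on | Latest (t = 21) | Beyond a Day 21 call |
|---|---|---|---|
| 1a | t + 21 | Day 42 | up to 21 days |
| Item 3 | t + 14 | Day 35 | up to 14 days |
| Item 4a | just after t + 7 | about Day 28 | up to about 7 days |
| 1b | Day 21 at latest | Day 21 | none |

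With the ±3-day margin, the maximum excess is 18 to 24 days for 1a and 11 to 17 days for item 3.

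Onset days (1 to 21) already decided at the call:
- 1a: t + 21 ≤ 21 gives 0 of 21. At a Day 24 call, t ≤ 3 gives 3 of 21 (14%).
- Item 3: t + 14 ≤ 21 gives t ≤ 7, or 7 of 21 (33%). At Day 24, t ≤ 10 gives 10 of 21 (48%).

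These describe one patient. They are not probabilities, because the documents give no distribution of onset times.

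**3. What the stagger does at the first gate.** The 0/3 or 1/3 count needs patient 3's assessment.
- *Patient 2, patients 2 and 3 both first dosed on Day 14.* Counted from patient 2's PVSRIPO, patient 3's call falls on Day 21 + 14 + 21 = 56 or later. Patient 2's latest 1a decision is 14 + 21 + 21 = Day 56. The clock has just run out. It falls short if patient 2 was dosed later after PVSRIPO than patient 3 (by at most 28 − 14 = 14 days) or if patient 3's call is early in the ±3 margin, unless a longer stagger makes up the difference.
- *Patient 1.* Even if patient 1 was dosed on Day 28 and patient 3 on Day 14, the call falls on 42 + 14 + 21 = Day 77 or later, against 28 + 42 = Day 70. The clock has always run out.
- *Patient 3.* Own call at Day 21 (±3), own 1a decision as late as Day 42. Exposed.
- *Patients 4 to 6.* No stagger among them. Exposed at the x/6 gate.

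**4. Which events are affected.** An event that brings debulking in the window, or that is treatment-related and leads to hospitalization, meets another serious criterion or is a Grade 4 non-hematologic toxicity, is a DLT at once. What remains is a Grade 3 event meeting none of these. Example: patient 3, onset on Day 12. Criterion 1a is decided on Day 12 + 21 = 33 and item 3, if it applies, on Day 12 + 14 = 26. Both fall after the latest allowed call, Day 24.

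**5. Effect on the gate.** From 0/3, one more counted event gives 1/3: three more evaluated patients, no halt. Under Section 3.1, one event changes continue to halt only where the count already stands at 1/3 or 2/6.

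**The case against.** The strongest reply is that the 21 days limit onset only. In criterion 1 the 3-week phrase attaches to the event, non-resolution has its own clock, and Section 3.1 asks whether a DLT occurs, not whether one is confirmed by Day 21. That is a sensible reading. It does not fit Section 7.4's statement that assessment runs until 21 days, or the word final at Visit 6, so the sections need reconciling under either reading.

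Three further points stand and limit the concern. The stagger lets the clocks of patients 1 and 2 finish on schedule. The immediate criteria catch many severe events. The data are collected: adverse events are followed to outcome (Section 7.1), and Visit 7 at Week 8 falls on 56 − 14 = Day 42 after an on-schedule first dose, when the latest 1a event becomes decidable. What is missing is a rule linking that information to the count.

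The DSMB reviews the lead-in and can recommend against continuing, and its charter prevails over the protocol (Section 9.3). The charter was not provided and may hold a rule for open events. As the protocol describes it, the review follows the same DLT assessment.

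A reader might infer that an open event is scored as no DLT and that full enrollment then opens, or that 1a can almost never be met by the decision date. The documents do not support either. No section states how an open event is scored, and the second inference applies one-patient figures to a gate that waits for three staggered patients.

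**Conclusion.** The conflict is real but narrow. The assessment called final can close up to 21 days before criterion 1a, and up to 14 days before item 3, can be decided; 1b needs no extra time. Read literally, a Grade 3 event that meets no immediate criterion and is still open has not met the DLT definition when the count is taken, and neither the protocol nor the SAP says how to treat it. On schedule this matters for patient 3 at the first gate and for patients 4 to 6 at the second.

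The dates rest on treatment starting at onset and on the stated visit schedule. Frequency cannot be derived. Putting an assumed share of missed DLTs through the gate rule for every patient would ignore the stagger, and the documents give no such share. Any uncounted event would lower the count and so favor proceeding, but the size of that effect is unknown.

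The wait before patient 4, which runs from patient 3's PVSRIPO infusion, is a separate matter. Correcting it alone would leave this gap in place.

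**What to change.** Reconcile Sections 3.1, 5.3.2 and 7.4 on three points:
1. The 21 (±3) days define the window in which an event must start.
2. An in-window event whose clock, as stated in Section 7.4, is still running at that date is recorded as pending.
3. The 0/3, 1/3 or x/6 count is taken only when no event is pending.

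Check the DSMB charter for a rule on this and align it. Carry the same classification into SAP Section 3.2.6, so that the reported DLT table matches the count used at the gate. No dose, treatment or grading rule has to change.

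The cost is a few words in each place and a wait of up to about 3 weeks before the gate decision, incurred only when an event is open at Day 21.

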**Exceptions (these laboratory values are DLT):**

- Grade 4 thrombocytopenia of any duration
- Grade 3 thrombocytopenia associated with bleeding requiring a platelet transfusion

5. Febrile neutropenia meeting following criteria:
  - a. Grade 3: ANC  $<$  1000/ $\mu$ l with a single temperature of  $>$  38.3° C (101° F) or a sustained temperature of  $\geq$  38° C (100.4 degrees F) for  $\geq$  1 hour
  - b. Grade 4: ANC  $<$  1000/ $\mu$ l with a single temperature of  $>$  38.3° C (101° F) or a sustained temperature of  $\geq$  38° C (100.4° F) for  $\geq$  1 h, with life-threatening consequences and urgent intervention indicated

## 7.5 Adverse Events of Special Interest

### 7.5.1 Cerebral Spinal Fluid Leakage or Aseptic Meningitis

Based on communications with the FDA agreed upon in IND 014735, Serial Submission 0197, in the event 2 or more patients enrolled under the current inclusion/exclusion criteria relating to catheter placement, present with evidence of cerebral spinal fluid leakage or aseptic meningitis, enrollment of patients under these criteria will be paused for further evaluation. The previous criteria (ie, catheter tip placed  $\geq 1$  cm from the ventricle and corpus callosum) will be used for continued enrollment until this evaluation is complete. These events will not be considered DLT for the purpose of evaluating PVSRIPO followed by pembrolizumab use unless further evaluation suggests an association.

### 7.5.2 Cerebral or Peritumoral Edema

Peritumoral edema (and possibly the signs and symptoms thereof) is considered expected with PVSRIPO therapy in rGBM based on the mechanism of action, whereby a targeted anti-tumor inflammatory immune response is elicited in and around the tumor. For the recommended best practices to manage signs symptoms related to PTE or CE, see [Section 6.5.4](#) (eg, low dose bevacizumab [7.5 mg/kg q 3 weeks] or dexamethasone [ $\leq 4$  mg/day], along with initiation of other supportive care treatments, as required [eg, antiepileptics]).

Peritumoral or CE may also be secondary to the disease process itself, the surgical procedure, necrosis from previous radiation, or inflammation due to immune infiltration of the brain or destruction of tumor cells, which may manifest as neurologic dysfunction. The timing of onset of such events should be considered in relation to PVSRIPO or pembrolizumab infusion when considering attribution of such events to these therapies (see PVSRIPO IB for guidance).

Peritumoral or CE may present as a constellation of general signs and symptoms such as altered mental status, cognitive disturbance, confusion, somnolence, lethargy, fatigue, unresponsiveness, encephalopathy, or coma or can be more focal, depending on the patient and tumor. The individual signs and symptoms may include but are not limited to: seizures, dysphasia, paresthesia, headaches, focal neurologic deficit, ataxia, dystonia, facial muscle weakness, hemiparesis, pyramidal tract syndrome, hemianopia, visual field cut, blurred vision, diplopia, and urinary incontinence. Participants will be monitored throughout the course of the study and upon noting any signs or symptoms of PTE or CE, may receive an antiangiogenic agent (bevacizumab), steroids, receive an osmotic diuretic, and/or have surgical decompression. Edema that fails to respond to aggressive therapy may lead to permanent neurological impairment. The probability of this risk can be predicted to some degree based upon tumor size, location,

preoperative neurological impairment, and post-operative course prior to virus administration. The risks will be discussed with the patient and the patient's family.

SAEs considered related the local inflammatory effect on the tumor (ie, peritumoral edema) should be reported in a way that distinguishes it from a more generalized brain edema (eg, "edema cerebral (peritumoral)". In cases where the edema is more generalized, reporting as "edema cerebral" would be more appropriate. In each case, the appropriate severity grade of the PTE or CE and the resulting symptoms/specific dysfunction should be noted in the edema-specific AE/SAE collection forms (and narrative description for SAE related to PTE or CE) by severity grade along with other relevant information (eg, start and stop date of each sign/symptom and any other information considered relevant by the investigator). Any signs or symptoms considered to be out of proportion to the extent of the PTE may be reported as additional SAEs, if indicated.

Except in cases of imminent life-threatening emergency, investigators should consult with the Sponsor Medical Monitor or designee is recommended prior to implementing anti-tumor treatments beyond the protocol-recommended supportive care options.

Delays and or discontinuation of pembrolizumab treatment should occur as outlined in **Sections 5.3** and **7.5.3** for events related to PTE and CE.

